4 STUDY OBJECTIVE

4.1 Primary Objective

The primary objective of the study is to evaluate the safety of CSF-1 compared with vehicle in presbyopic subjects.

4.2 Study Hypothesis

CSF-1 ophthalmic solution (0.4% pilocarpine hydrochloride) has an acceptable safety profile when used in healthy adults with a history of presbyopia.

5 OVERALL STUDY DESIGN

This is a 4 visit, multi-center, double-masked, vehicle-controlled study evaluating the long-term safety of CSF-1 compared to vehicle in a total of approximately 170 subjects with presbyopia (approximately 113 subjects assigned to CSF-1 and approximately 57 subjects

[REDACTED]

[REDACTED]

[REDACTED]

[REDACTED] All subjects who have not completed Visit 4 at the time of Protocol Amendment 2.0 approval will proceed with the scheduled visits until study exit at Visit 4 (Week 6). All subjects treated beyond Visit 4 at the time of Protocol Amendment 2.0 approval [REDACTED] will proceed to study exit at the next scheduled study visit ([REDACTED]). The maximum timepoint for these subjects to exit the study will be Visit 7 (Week 21). All subject data will be analyzed for all measured timepoints, including data from subjects treated beyond Visit 4.

Subjects will be consented and study eligibility will be determined at Visit 1 (Screening). Subjects who remain eligible after Visit 1 will return for Visit 2 (Baseline Visit) to be assessed for randomization into the study. If eligible, subjects will be enrolled in this safety study and randomized 2:1 to receive CSF-1 or vehicle bilaterally. All study treatments are topical ophthalmic solutions that should be administered bilaterally. The initial dose will be instilled during Visit 2 after completing the visual acuity assessment. Subjects will be instructed to instill with a single drop in each eye (OU) twice daily (BID) at approximately 2-to-3-hour intervals later. Subjects would be reminded not to dose at home on clinic visit days. Medical history updates and adverse event assessments will be done at this and subsequent visits. Investigational product and dosing diary will be dispensed to subject. Subject will be instructed to return to clinic at the next scheduled visit.

5.1 Dose Regimen

Enrolled subjects will be randomized 2:1 to receive CSF-1 or vehicle bilaterally. Subjects will be instructed to dose one drop in each eye, twice daily (BID), at 2 to 3 hours intervals (OU). This regimen should be followed daily. Subjects who have not completed Visit 4 (Week 6) at the time of Protocol Amendment 2.0 approval will dose for at least 6 weeks. Subjects treated beyond Visit 4 at the time of Protocol Amendment 2.0 approval will dose until the next scheduled visit (████████) and exit the study. Subjects must avoid dosing prior to visit on the day of a visit. If subjects dose prior to their visit, the study visit will be rescheduled.

6 STUDY POPULATION

6.1 Number of Subjects

This study will enroll approximately 170 subjects (approximately 113 subjects assigned to CSF-1 and approximately 57 subjects assigned to vehicle) into the trial.

All subjects who have not completed Visit 4 (Week 6) at the time of Protocol Amendment 2.0 approval will be treated for at least 6 weeks and complete 4 study visits. All subjects treated beyond Visit 4 at the time of Protocol Amendment 2.0 approval will continue to be treated and exit the study at the next scheduled visit.

6.2 Study Population Characteristics

The study will include healthy adult subjects between 40 and 64 years of age with presbyopia who do not have any conditions, in the investigator's opinion, that may put the subject at increased risk, confound study data, or interfere significantly with the subject's study participation.

6.3 Inclusion Criteria

Subjects must:

1. Be able and willing to provide written informed consent and sign a Health Information Portability and Accountability Act (HIPAA) form prior to any study procedure being performed;
2. Be able and willing to comply with the study requirements and attend all study visits;
3. Be 40-64 years of age of either sex and any race or ethnicity and must be in general healthy condition at Visit 1;
4. ██████████
5. ██████████
6. Have a negative serum pregnancy test result at Visit 1, if female is of childbearing potential (those who have experienced menarche and who are not surgically sterilized [bilateral tubal ligation, hysterectomy, or bilateral oophorectomy] or post-menopausal [12 months after last menses]) and must use

adequate birth control throughout the study period. Adequate birth control is defined as hormonal – oral, implantable, injectable, or transdermal contraceptives; mechanical – spermicide in conjunction with a barrier such as condom or diaphragm; intrauterine device (IUD); or surgical sterilization of partner. For non-sexually active females, abstinence may be regarded as an adequate method of birth control;

7. Be able and willing to avoid all disallowed medications for the appropriate washout period and during the study without significant risk to the subject;
8. Have natural lens (phakic) in both eyes.

6.4 Exclusion Criteria

Subjects must not:

1. Be a female of childbearing potential who is currently pregnant, nursing, or planning a pregnancy;
2. Have known contraindications or sensitivity to the use of any of the study medications or their components;
3. Have an active ocular infection at Visit 1 (bacterial, viral, or fungal), positive history of an ocular herpetic infection, preauricular lymphadenopathy, or ongoing, active ocular inflammation (e.g., moderate to severe blepharitis, allergic conjunctivitis, peripheral ulcerative keratitis, scleritis, uveitis) in either eye;
4. [REDACTED]
5. [REDACTED]
6. Have any clinically significant abnormal findings on systemic labs (i.e., hematology, blood chemistry analysis, and urinalysis) at screening. If a laboratory finding is outside the normal limits, clinically significant abnormal findings will be determined by the investigator.
7. Have clinically significant abnormal findings (e.g., clinically significant cataract, central corneal scar) on a slit lamp biomicroscopy exam in either eye documented at screening/baseline or a known history of a clinically significant slit-lamp finding in either eye at Visit 1;
8. Have intraocular pressure (IOP) [REDACTED] or have a prior diagnosis of ocular hypertension or glaucoma or currently being treated with any type of topical IOP lowering (glaucoma) medication at Visit 1;
9. Have any clinically significant abnormal findings on dilated indirect fundus exam in either eye at screening or undilated fundus exam in either eye at baseline or a known history of retinal detachment, retinal tears, or clinically significant retinal disease in either eye;

10. Have a known history or diagnosis in the past of: iritis, scleritis, or uveitis, whether active or inactive;
11. Have had surgical intervention (ocular or systemic) within 1 year prior to Visit 1, or a planned surgical intervention within 30 days after the study exit visit;
12. [REDACTED]
13. Have completed participation in an investigational drug or device study within 30 days of Visit 1;
14. Use any of the following prohibited systemic medications during the timeframe noted below:
 - a) The day of the study visit or within 12 hours prior to a study visit (chronic, daily use is not allowed):
 - i. Nonsteroidal anti-inflammatory drugs (NSAIDs) (e.g., Advil®, Motrin®) except for once daily Aspirin used in (cardiovascular) prophylactic dose of 81 mg. Topical NSAIDs are allowed.
 - ii. narcotic (opiate class) pain medication (e.g., codeine, OxyContin®, Vicodin®, Tramadol®)
 - b) Two (2) weeks (14 days) prior to Visit 1 and for the duration of the study:
 - i. bladder medications (cholinergics [e.g., Urecholine®, bethanechol], anticholinergics [e.g., oxybutynin] and antimuscarinics [e.g., fesoterodine])
 - ii. attention-deficit/hyperactivity disorder (ADHD) medications
 - c) During the year preceding the enrollment in the study and during the entire duration of the study:
 - i. Any antipsychotics
 - ii. Any antidepressants
15. Have a diagnosis of unstable diabetes mellitus (i.e., A1C levels less than 4% or greater than 6%) or a history of elevated blood sugar as reported by the patient;
16. Have a condition or a situation, which, in the Investigator's opinion, may put the subject at increased risk, confound study data, or interfere significantly with the subject's study participation, including but not limited to unstable cardiovascular, hepatic, renal, respiratory, gastrointestinal, endocrine, immunologic, dermatologic, hematologic, neurologic, or psychiatric disease.
17. Have previously participated in CSF-1 clinical trial;
18. Be currently using any topical ophthalmic medications that may confound safety data (e.g., Vuity®, Latisse®, Upneeq®, Lumify®) and not be able to discontinue these medications for the duration of the trial (excluding medications allowed for the conduct of the study); the respective wash-out periods are required for

the following medications:

- a) Latisse®, Upneeq®, Vuity®, and Lumify®: 14 days prior to Visit 1

6.5 Withdrawal Criteria

Subjects will be withdrawn from the study if any of the following criteria are met:

- Be a female of childbearing potential who is currently pregnant, nursing, or planning a pregnancy; tests positive to a urine pregnancy test or refuses to use an adequate method of contraception for the duration of the study;
- Have an active ocular infection (bacterial, viral, or fungal), active ocular inflammation (e.g., moderate to severe blepharitis, allergic conjunctivitis, peripheral ulcerative keratitis, scleritis, uveitis) at any visit in either eye.
- Subjects may also be withdrawn from the study for the following reasons:
 - Adverse event (AE)
 - Lost to follow-up
 - Withdrawal of consent by subject
 - Investigator's discretion
 - Death
 - Subject not adequately following required study procedures
 - Study terminated by the Sponsor
 - Other

Subject withdrawals will be documented on the subject's source document.

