9.4.2 Unscheduled Visits

In the case of an AE, an unscheduled visit may occur. The investigator may perform additional assessments at their discretion. All additional assessments will be documented in the subject's source document.

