9.6.2 Withdrawn Subjects

A subject may be withdrawn for meeting any of the withdrawal criteria as described in [Section 6.5](#).

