10.4 Procedures for Unmasking

When medically necessary, the investigator may need to determine what treatment has been assigned to a subject.

In an emergency situation, where knowledge of the study drug treatment is critical to the study safety, the code may be broken. Study Treatment should remain masked to the CRO, study monitor (CRA) and Sponsor.

The Investigator should determine if the situation is a medical emergency (ocular or non-ocular) and whether the knowledge of the treatment is critical to subject safety. The Investigator should attempt to contact the Medical Monitor prior to unmasking the study treatment if possible. If unmasking is necessary, only the Primary Investigator will have the appropriate level of access in order to perform the unmasking within the [REDACTED] Clinical One Interactive Response Technology (IRT) System. The Primary Investigator will select the subject, follow the prompts to “Manage Subject” and then select the “Code Break” option. During this process, the Primary Investigator will be asked to confirm each step as well as whether the unmasking is related to an adverse event. Once all confirmatory questions are answered, the subject’s treatment arm will be unblinded and the treatment arm will be displayed for the subject along with the assigned kits. For step-by-step details on Emergency Unmasking procedures, please refer to the IRT Training Plan.

The investigator must notify the Medical Monitor and the Study Monitor as soon as possible after unmasking. In addition, the Investigator must record the date, time and

reason for unmasking the study drug treatment in the source documentation, however, the subject treatment must NOT be recorded in the source documents. The unmasked subject must be discontinued from study.

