11.6 Safety Analysis

All safety data will be analyzed using the safety set. Safety of CSF-1 compared to vehicle will be assessed by the review of all safety parameters.

Verbatim descriptions of AEs will be mapped to Medical Dictionary for Regulatory Activities (MedDRA) terms and be presented in a data listing. Treatment emergent AEs (TEAEs) is defined as any event not present prior to the initiation of the drug treatment or any event already present that worsens in either intensity or frequency following exposure to the drug treatment. TEAEs will be summarized by treatment group using frequency and percent for each system organ class (SOC) and preferred term (PT) within each SOC. The

number of AEs, TEAEs, serious TEAEs, and TEAEs causing premature discontinuation will be provided by treatment group. In addition, the frequency and percentage of subjects with at least one AE, at least one TEAE, and at least one serious TEAE will also be provided by treatment group.

Similar summaries will also be presented for TEAEs related to the study drug, by severity, and by study day of onset. When reporting the incidence of AEs, a subject will only be counted once if they ever experience an event within the SOC and ever experience the individual PT within each treatment group. The number of AEs as well as the incidence rate over the study period will also be summarized.

Changes from baseline in vital signs, BDCVA, LL-BDCVA, slit lamp biomicroscopy, IOP, and dilated indirect fundus examination and endothelial cell density will be summarized descriptively for at each visit by treatment group. Changes from baseline in endothelial cell density parameters will be tested between treatment groups using two-sample t-tests.

The categorical summaries for the loss of ≥ 0.2 logMAR from baseline (yes/no) and for the loss of > 0.2 logMAR (yes/no) in BDCVA and LL-BDCVA at each visit will also be presented and compared between treatment groups using Pearson chi-squared test or Fisher's exact test if any cell counts are less than 5.

Full details of the safety analyses will be specified in the formal Statistical Analysis Plan.

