11.8 Missing Data

There will be no imputations for missing data.

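### Subjects withdrawn for ocular infection or inflammation drop out of later by-visit tables, which could understate eye findings; add a worst post-baseline summary by arm

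*Combined protocol and SAP*

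**What the plan says.** **Exit from the study.** Section 6.5 reads "Subjects will be withdrawn from the study if any of the following criteria are met". One listed criterion is "Have an active ocular infection (bacterial, viral, or fungal), active ocular inflammation", at any visit and in either eye. Section 9.6.2 is weaker: "A subject may be withdrawn for meeting any of the withdrawal criteria". Section 10.4 adds: "The unmasked subject must be discontinued from study".

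**Missing values.** Section 11.8: "There will be no imputations for missing data".

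**Analysis.** Under Section 11.6, changes from baseline in vital signs, BDCVA, LL-BDCVA, slit lamp, IOP and dilated fundus "will be summarized descriptively for at each visit by treatment group". The Synopsis list also names fluorescein staining. Loss of at least 0.2 logMAR, and of more than 0.2 logMAR, in BDCVA and LL-BDCVA "at each visit will also be presented and compared between treatment groups using Pearson chi-squared test", or by Fisher's exact test when cells are small.

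**Timing.** Sections 7.1 and 11.3 place physical examination, vital signs, systemic labs and the dilated fundus exam at Visit 1 and at Visit 4, or at the later exit visit for subjects already past Visit 4.

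**Provisions that soften the effect.** Section 9.6.3 asks sites to gather what follow-up data they can before discontinuing a subject. Section 10.5 follows unresolved adverse events to resolution. Section 11.2 keeps every dosed subject and all collected data in the safety set. Section 11.6 counts a subject who ever had an event and tabulates TEAEs that led to discontinuation.

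**The concern.** Safety against vehicle is the trial's only objective, and ocular inflammation is one of the outcomes that bear on it. Section 6.5 makes that outcome a reason to leave the study, not only to stop dosing. The later tables are then computed on those who remain, and whether a subject remains depends partly on what the table measures. A descriptive table or chi-squared test on the remaining subjects at Visit 4 could show fewer ocular findings than the randomised groups had. If exits of this kind differ between arms, the comparison could shift as well.

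The mechanism is not far-fetched for this drug. Section 3 says diclofenac was first combined with pilocarpine to reduce an inflammatory response associated with pilocarpine.

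**Working it through.** **1. The plan's own figure.** The Synopsis gives at least 95% probability of detecting an adverse event with a rate of 2.66% among 113 CSF-1 subjects treated for at least six weeks. 1 − (1 − 0.0266)^113 = 0.9525, so the figure reproduces and is not in dispute. It needs ln 0.05 / ln 0.9734 = 111.1, that is 112 subjects. With 107 six-week subjects the probability would be 94.4%, and the rate detectable with 95% probability 1 − 0.05^(1/107) = 2.76%. A few early exits barely move this statement. The exposure lies in the by-visit tables.

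**2. Which tables are exposed.**
- The visit at which the infection or inflammation is found stays in the tables. Only later visits are affected.
- After Amendment 2 most subjects have two post-baseline visits, Week 2 and Week 6. For them the exposed table is Visit 4, plus Visit 3 if the subject left earlier at an unscheduled visit. A subject first found at the exit visit loses nothing.
- Vital signs, physical examination, systemic labs and dilated fundus have their only planned post-baseline assessment, in the visible text, at the exit visit. A subject withdrawn at Visit 3 may have no post-baseline value for any of them.

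**3. Illustration.** The documents give no withdrawal rate, so every count here is assumed except the arm sizes, 113 and 57 (Section 11.4). Suppose 8 of 113 CSF-1 subjects and 0 of 57 vehicle subjects would show a finding at Visit 4, and k of the 8 leave before it. The Visit 4 table shows (8 − k)/(113 − k).

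| k withdrawn | CSF-1 at Visit 4 | Fisher p against 0/57 |
|---|---|---|
| 0 | 8/113 = 7.1% | 0.053 |
| 2 | 6/111 = 5.4% | 0.097 |
| 4 | 4/109 = 3.7% | 0.30 |
| 6 | 2/107 = 1.9% | 0.54 |

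If the finding was recorded before exit, a per-subject worst post-baseline table returns 8/113 = 7.1% in every row.

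**4. Direction.** Take 6/113 against 1/57 (5.3% against 1.8%). If four of the six CSF-1 subjects leave, Visit 4 shows 2/109 = 1.8%, equal to vehicle. If instead the one vehicle subject leaves, it shows 6/113 = 5.3% against 0/56 = 0%, and the difference widens from 3.6 to 5.3 percentage points. The same rule can shrink or inflate the contrast.

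**The case against.** The strongest reply is that the report does not lose these subjects. Section 10.1 makes any clinically relevant deterioration a recordable adverse event, the TEAE tables count subjects who ever had one, and TEAEs causing discontinuation are shown by arm. A reader might infer that harmed subjects disappear from the safety evaluation. The documents do not support that, and this part of the reply stands in full.

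A reader might also infer that the comparison is biased in favour of CSF-1. Nothing in the documents establishes it. Section 3 reports slit-lamp, BDCVA and IOP changes comparable between arms in both earlier Phase 3 studies, and says diclofenac did not significantly improve safety. The illustration takes one-sided withdrawals, treats the finding as a withdrawal trigger although Section 6.5 requires active infection or inflammation, and assumes the finding would still be present at Visit 4. Unmasked subjects need not have been harmed at all: Section 10.4 covers ocular and non-ocular emergencies alike.

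A third inference would be that findings at unscheduled visits never reach the database, because Section 9.4.2 says "All additional assessments will be documented in the" source document and does not name the eCRF. Section 12.6 already requires complete eCRF recording, so no separate remedy is needed.

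Finally, the per-visit procedures and visit schedule are redacted or not shown, and Section 11.6 leaves full details to a formal SAP. An early-exit assessment or a worst-value table may be specified there, which cannot be checked. What remains is that Section 9.6.3 is a best-effort request that names no assessments, and the visible analysis text does not say how values obtained at early exit enter a by-visit table.

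**Conclusion.** The concern holds in limited form. Following the visible text, tables and tests for visits after a withdrawal, mainly Visit 4, could understate ocular findings, and more so in an arm with more such withdrawals. The four measures planned only at exit may have no post-baseline value for subjects who leave early. Adverse event reporting limits the consequence to the by-visit tables and tests.

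Neither size nor direction can be derived from the documents. The fall from 7.1% to between 5.4% and 1.9% rests wholly on assumed counts, and shows only that with small numbers a handful of exits can remove most of a signal from one table. Separately, Sections 6.5 and 9.6.2 disagree on whether withdrawal is mandatory. They must be reconciled, since sites could otherwise apply the exit differently.

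**What to change.** Add to Section 11.6 and the SAP:

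- A per-subject worst post-baseline summary by arm on the safety set, for BDCVA and LL-BDCVA (including both logMAR loss categories), slit lamp, fluorescein staining and IOP, using scheduled, unscheduled and early-exit values.
- The number of missing values, and the reasons, at each visit by arm. This should include the measures assessed only at exit, whose missing values a worst-value table cannot recover.

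Reconcile Sections 6.5 and 9.6.2.

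The cost is a few extra tables and no new visits. Worst-value summaries pick up more transient findings, in both arms, so they belong beside the by-visit tables and not in their place.

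Optionally, separate stopping study drug from leaving the study, so that subjects withdrawn for ocular findings may attend the remaining scheduled safety assessments, with off-drug data flagged. This costs a few visits. It should not extend to unmasked subjects, whose investigator knows the arm, and it leaves the treatment-stopping rules unchanged.

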7 STUDY PARAMETERS

7.1 Safety Measures

Safety will be assessed by the following measures for all subjects:

- Adverse events (AE) (reported, elicited, and observed)
- BDCVA (best distance-corrected visual acuity)
- Low-luminance BDCVA (LL-BDCVA)
- Slit lamp biomicroscopy
- Fluorescein staining
- IOP
- Undilated fundus exam at Visit 2 Baseline (Week 1/ Day 1)

- Serum pregnancy test at Visit 1 Screening and Urine pregnancy test at Visit 4 (Week 6) or next scheduled visit (study exit) for subjects treated beyond Visit 4 at the time of Protocol Amendment 2.0 approval (for females of childbearing potential)
- Physical examination at Visit 1 Screening and Visit 4 (Week 6) or next scheduled visit (study exit) for subjects treated beyond Visit 4 at the time of Protocol Amendment 2.0 approval
- Vital signs (resting blood pressure and pulse) at Visit 1 Screening and Visit 4 (Week 6) or next scheduled visit (study exit) for subjects treated beyond Visit 4 at the time of Protocol Amendment 2.0 approval
- Systemic labs: hematology, blood chemistry analysis, and urinalysis at Visit 1 Screening and Visit 4 (Week 6) or next scheduled visit (study exit) for subjects treated beyond Visit 4 at the time of Protocol Amendment 2.0 approval
- Dilated indirect fundus exam at Visit 1 Screening and Visit 4 (Week 6) or next scheduled visit (study exit) for subjects treated beyond Visit 4 at the time of Protocol Amendment 2.0 approval

